Study participants will receive information about the development of antibodies against SARS-CoV-2, with an IgG test used in clinical routine in the Stockholm Region. This test cannot distinguish between antibody formation after vaccination or SARS-CoV-2 infection, but since we perform SARS-CoV-2 antibody serology and PCR tests at baseline, as well as SARS-CoV-2 PCR tests for COVID-19 symptoms during the study period, it is highly likely that those who seroconvert without a diagnosis of COVID-19 do so because of vaccination. Other than that, there's no direct benefit for participants to take part in the immunological evaluation in the study, but knowledge that can be generated at the group level can indirectly benefit participants, as it can give a deeper indication of immunity in the group with the current diagnosis. This is because patients with immunosuppression are considered to be at risk for severe COVID-19 and may potentially have a reduced response to the COVID-19 vaccine compared to people without immunodeficiency. As these individuals have generally not been included (except for a few HIV-infected individuals) in previous clinical trials of Comirnaty or other mRNA-based vaccines, there is a knowledge gap. The study will give us a better understanding of the immunological response after vaccination with mRNA-based COVID-19 vaccines, both on the humoral and cellular sides. This may lead to better mechanistic knowledge of whether specific parameters correlate with a poorer adaptive immune response or protection after vaccination. For society, vaccines not only protect the individuals who receive them, but can also potentially reduce the risk of developing mutations that can occur in people with compromised immune systems after SARS-CoV-2 infection and prolonged replication of the virus.

The extended study (version 5.0), which only involves blood sampling, is not expected to pose any significant risk to the research subjects, as sampling in the most severely ill groups is performed frequently in routine healthcare without any significant risks, except for possible risks of local bleeding, which usually stops spontaneously.

The study will be extended by two additional visits, at month 30 and month 36 (version 7.0), and will involve research subjects providing blood and saliva samples on these occasions and stool samples (for the HIV group and healthy controls) at month 36 after renewed consent.

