4. OBJECTIVE AND ENDPOINTS

4.1. Objective

The primary objective is to investigate the immunological effect of Comirnaty by measuring the incidence of seroconversion (development of antibodies against SARS-CoV-2 upon vaccination in seronegative individuals) after 2 vaccine doses.

Secondary objectives:

- To evaluate safety and tolerability of the given vaccine in the research subjects.
- To measure the incidence of SARS-CoV-2 infection documented by a positive PCR test during the study period.

Exploratory objectives:

- Proportion (95% CI) seroconverting to a positive response to SARS-CoV-2 IgG serology after two doses of vaccine, at 9 months, 12 months, 18 months, 24 months, 30 months, and 36 months after the second vaccine dose. This may mean that patients in routine healthcare have received one or more additional vaccine doses depending on the recommendations of the Public Health Agency of Sweden.
- To investigate the humoral response in more detail and analyze the cellular immune response after the vaccine has been administered.
- To examine the virus genome in breakthrough infections of SARS-CoV-2.
- To evaluate the importance of the oral and intestinal microbiome for vaccine efficacy in HIV-infected individuals.

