- HIV-infected individuals and control subjects are offered participation in a study component investigating the significance of the microbiome for vaccine efficacy. Individuals who agree to participate in this component will be sent fecal sample collection kits to their homes after the video visit, or the kits will be given to them directly during the physical visit. The person can then send the fecal sample by mail to the study unit during the screening period, or drop it off on site on day 0, before or after the injection of the first vaccine dose. Saliva samples submitted in the study can be used for both antibody response and oral microbiome analyses.

5.2.2. Day 0

If study participants meet all inclusion criteria and no exclusion criteria, they can proceed to day 0, either on the same day or on another day within 28 days after screening. Day 0 visits take place at the study unit.

On day 0, the first vaccine dose is given according to the product summary, and the vaccination is registered in an internet-based reporting system for vaccinations according to healthcare routine (Vaccinera). The study unit where vaccinations are planned to be given will have the necessary equipment and medicines (adrenaline, cortisone, and antihistamine) on hand for a potential anaphylactic reaction. A doctor will be available.

Individuals with an increased risk of bleeding, such as known coagulopathy or anticoagulant treatments, will be managed according to section 5.3.1.

Day 0 samples will be taken before injection of the first dose of vaccine. Sampling according to the schedule in Table

2. For blood sample volume at each visit and total in the study for each subgroup of study participants, please see Appendix 2). Saliva will be collected by having study participants spit saliva into a clean jar for 5 minutes. It is also possible to provide a saliva sample after the vaccine dose.

Two groups of sampling are planned:

A. Group with sampling without cellular immunity.

B. Group with cellular immunity sampling (at least 40 study participants per patient group)

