5.5.2. Medical history and medications

Medical history, only ongoing drug treatments for the underlying disease, and recently completed immunosuppressive treatment (i.e., <4 weeks from inclusion) are recorded at the screening visit. Ongoing immunosuppressive treatments are divided into steroid and non-steroid treatments.

Specific treatments for individual patient groups are recorded at the screening visit as follows:

Patient group	Parameter
Patients with HIV infection	Antibiotic treatment during the last 3 months.
Patients who have undergone solid organ transplantation	Rejection treatment during the last 6 months. Thymoglobulin treatment during the last 12 months. Rituximab treatment during the last 12 months. Chemotherapy during the past 12 months.
Patients with CLL	Fludarabine (/cyclophosphamide (FC) in combination with rituximab (FCR) during the last 6-30 months. Bedamustine in combination with rituximab (BR) within the last 6-30 months. Rituximab-containing treatment during the last 6 months.

All new medications during the period from the vaccination date to 14 days after each vaccine dose are recorded (i.e., both after vaccine dose 1 and vaccine dose 2). The rationale for this time limit is that if certain adverse events occur during the AE observation period, an assessment must be made as to whether they are related to the study drug or another medication. Although no interaction studies have been conducted in previous clinical trials, we do not expect any drug interactions between the study drug and other drugs. We have already excluded individuals who are scheduled to receive any other vaccination in the exclusion criteria. However, any newly initiated immunosuppressive or immunoglobulin treatments after day 0 (screening) will be recorded, as this may affect the efficacy of the vaccine.

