6.3. Planned analyses

6.3.1. Descriptive analyses

- The number and percentage (95% CI) of study participants with co-morbidity and other baseline characteristics.
- Previous and ongoing treatments will be summarized.
- Description of abnormal findings on complete or targeted physical examinations, vital parameters, clinical laboratory tests, and pregnancy tests.

6.3.2. Analyses of primary endpoint:

- Proportion (95% CI) receiving a positive SARS-CoV-2 IgG serology test result after two vaccine doses, three weeks after the second vaccine dose in the "population with two doses of vaccine," and having a negative SARS-CoV-2 serology test result at baseline, i.e., seroconverting.
- Chi² test is used for comparisons with the control group.

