6.3.3. Analyses of secondary endpoints

- Proportion (95% CI) seroconverting to a positive response to SARS-CoV-2 IgG serology after two doses of vaccine, at 3 months and 6 months after the second vaccine dose, measured in the "two-dose vaccine population" compared with the control group.
- Proportion (95% CI) experiencing adverse events, with AE/SAE/SUSAR. Number and proportion (95% CI) experiencing local reactions and systemic reactions are measured in the "Full analysis set population".
- Proportion (95% CI) receiving a new diagnosis of SARS-CoV-2 infection through a positive PCR test is measured in the "Full analysis set population."

- Comparisons are made with the control group.

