11. APPENDIX

11.1 Appendix 1 - List of parameters for screening visits and during the study period for eCRF

A base module is created for all patients, followed by specific modules for each patient group. The "healthy controls" group has its own base module in eCRF.

Base module: All patients (primary population)

Gender:

M/F Age:

Diagnosis for inclusion: (Primary immunodeficiency/HIV/allogeneic stem cell transplantation or CAR T cell therapy/Solid organ transplantation/CLL)

Immunosuppressive treatment in the last 4 weeks prior to inclusion: yes/no Ongoing medication at inclusion:

- Non-immunosuppressive drugs: yes/no, if yes, which ones
- Ongoing immunosuppressive treatment, steroid: yes/no, if yes, for how long
- Ongoing immunosuppressive treatment, non-steroid: yes/no, if yes, which

Patient group 1. Patients with primary immunodeficiency

Primary diagnosis:

Confirmed genetic mutation: yes/no, if yes, which gene?

Other comorbidities relevant to vaccine response: yes/no (if yes, describe)

Malignancy: yes/no, if yes, describe which?

Lung disease: yes/no, if yes, describe which?

Autoimmune disease: yes/no, if yes, describe which? Immunoglobulin treatment: yes/no

Rituximab Yes/No. If yes: When was the last dose?

Patient group 2. Patients with HIV infection

Ethnicity: Caucasian, Black, Oriental, Latin, Other.

HIV diagnosis date:

Latest CD4: date, number, percentage Nadir CD4: date, number, percentage, Latest HIV

RNA:

Opportunistic infection: yes/no, if yes, which infection and date

Number of years of antiviral treatment:

Antiviral treatment: (which)

BMI:

Diet – normal diet/vegetarian/other: [if other, describe]

Antibiotic treatment during the last 3 months: yes/no, if yes, describe which antibiotic and duration.

Patient group 3. Patients who have undergone allogeneic stem cell transplantation/CAR T cell therapy

Primary diagnosis:

Stage of disease at transplantation Type of donor

Stem cell source Conditioning regimens GVHD prophylaxis

Acute GVHD Yes/No and severity Chronic GVHD Yes/No and severity

Ongoing immunosuppression (non-steroidal) Yes/No and type
Ongoing corticosteroid therapy Yes/No, severity, and type of medication Any significant opportunistic infection prior to vaccination (CMV, EBV, adenovirus, invasive fungal disease)
Previous rituximab Yes/No. If yes:
When? Obliterative bronchiolitis Yes/No

Patient group 4. Patients who have undergone solid organ transplantation/CAR T cell therapy

Primary diagnosis: Blood group

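### No analysis rule covers baseline-negative participants given immunoglobulin before a later sample, so passively acquired spike IgG could be counted as vaccine seroconversion, mainly at 3 to 36 months

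*Combined protocol and SAP*

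**What the plan says.** Section 6.3.2 takes the "Proportion (95% CI) receiving a positive SARS-CoV-2 IgG serology test result after two vaccine doses" and adds the condition "and having a negative SARS-CoV-2 serology test result at baseline, i.e., seroconverting". Section 4.1 agrees, defining seroconversion as "development of antibodies against SARS-CoV-2 upon vaccination in seronegative individuals". The baseline is a single sample: under 5.2.2, "Day 0 samples will be taken before injection of the first dose of vaccine". The assay detects IgG against the spike protein (5.4.1).

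Sections 3.2 and 5.5.9 both concede that the test cannot tell vaccination from infection. They name no third source of antibody. Section 3.2 concludes that "it is highly likely that those who seroconvert without a diagnosis of COVID-19 do so because of vaccination".

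Immunoglobulin is not among the exclusions in 5.1.4. Section 5.5.2 says that "any newly initiated immunosuppressive or immunoglobulin treatments after day 0 (screening) will be recorded, as this may affect the efficacy of the vaccine". Appendix 1 has a dedicated baseline item, "Immunoglobulin treatment: yes/no", in the primary immunodeficiency module only.

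In the analysis sections, 6.3.1 summarises previous and ongoing treatments. Sections 6.2, 6.3.2 to 6.3.4 and 6.4 contain no exclusion, stratification or sensitivity analysis by immunoglobulin use. The same definition of response carries through to 3 and 6 months (6.3.3) and to 9 to 36 months (6.3.4).

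**The concern.** The endpoint is meant to measure the participant's own response to the vaccine. The assay measures whether spike IgG is present, not where it came from. Infused donor IgG is a possible third source if the products contain anti-spike antibody. The negative baseline removes anyone already positive on day 0, but it cannot remove antibody infused afterwards, and that one sample is the only reference for results out to 36 months.

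The protocol recognises that immunoglobulin may matter to efficacy and collects it for that reason, but the analysis then ignores it. Section 6.1 calls the study descriptive or exploratory, so the group proportions and their confidence intervals are the main product. At stake is whether a positive result in a treated patient, particularly a late one read as persistence, is described as a vaccine response when it may not be one.

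**Working it through.** **The plan's own figures.** The one calculated figure in section 6 is power above 80% at N = 540, effect size 0.15 and alpha 0.05. Read as Cohen's w with 1 degree of freedom, the noncentrality is 540 × 0.15² = 12.15 and the power is about 93.7%, so the figure reproduces on that reading. It does not depend on immunoglobulin. The 2-week seroconversion rates in 2.1 (72% of all patients, 43% organ transplant, 63% CLL) come without counts and cannot be recomputed.

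**Who can be misclassified.**
- Positive on day 0 from infused antibody: excluded by 6.3.2 and 4.1.
- Negative on day 0 and no immunoglobulin afterwards: unaffected.
- Negative on day 0, no vaccine response, immunoglobulin before the later sample, and made positive by it: counted as seroconverted. No rule covers this case.

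**Time available.** Dose 2 is on day 21 ± 3 and the primary sample 14 ± 3 days later, so the sample falls nominally on day 35, with a range of 29 to 41. (This uses the 2 weeks of 4.2 and 6.2; 6.3.2 itself says three weeks, which would be day 42.) Someone on regular replacement who tests negative on day 0 had no detectable passive antibody then, so for that person status must change within about five weeks. At 3 to 36 months the interval is far longer.

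**What the record can identify.** The base module for all patients asks which non-immunosuppressive drugs are ongoing. Footnote 4 to the visit schedule has all medications noted at screening, and 5.6.5 documents all concomitant drugs. Visit reviews from day 10 onward mention immunoglobulin by name. From month 9 only newly initiated courses are noted. Most users should therefore be identifiable; infusion dates and the later course of ongoing replacement are not.

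**Size, as illustration.** Let o be the observed proportion, p the vaccine-induced proportion and g the share of non-responders made positive by infusion. Then o = p + (1 − p) × g, so p = (o − g)/(1 − g). The 63% for CLL is an observed rate and enters as o. The documents do not give g. The assumed range of 5% to 30% corresponds to 10% of non-responders treated with half made positive (0.10 × 0.50), up to 30% treated with all made positive (0.30 × 1.00).

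| g (assumed) | p |
|---|---|
| 0 | 63% |
| 5% | (0.63 − 0.05)/0.95 = 61.1% |
| 15% | (0.63 − 0.15)/0.85 = 56.5% |
| 30% | (0.63 − 0.30)/0.70 = 47.1% |

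The gap is 1.9 to 15.9 percentage points, or about 2 to 14 patients in a group of 90. For comparison, the 95% half-width at 63% with n = 90 is 1.96 × √(0.63 × 0.37/90) = 10.0 points.

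**Effect on the comparison.** Take a vaccine-induced 72%, an assumed control rate of 99% and g = 25%. The patient rate becomes 0.72 + 0.28 × 0.25 = 79.0%, and power for 90 versus 90 is still 0.993. The estimate is affected much more than the test.

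**The case against.** The strongest reply is that the plan already requires a negative baseline, so a reader who inferred that any positive IgG result counts as seroconversion would be wrong. That stands, and it limits the problem to infusions after day 0.

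Second, nothing in the documents says that immunoglobulin products contain anti-spike IgG, or how many participants receive them. This also stands. One might infer that the patient rates in 2.1 are overstated; the documents support only that they could be. Nor can 63% be entered as the true response and bias added on top, because an observed rate would already include any bias.

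Third, the primary window is about five weeks, and any bias works against the lower patient response expected in 2.2. Both are right. The direction protects the conclusion that patients respond less, but not the estimated proportions.

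Fourth, sections 4.1, 4.2 and 2.2 already acknowledge that extra doses and new infections can influence the later results, so these are not presented as pure two-dose persistence. That is fair, but those acknowledgements do not mention infused antibody.

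Fifth, the medication record is fuller than the single dedicated field suggests. This stands too. It weakens a complaint about missing data and makes the absence of any analysis using the record easier to remedy.

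**Conclusion.** The gap is real but narrow: a baseline-negative participant who receives immunoglobulin before a later serology sample has no analysis rule, and 3.2 would attribute a resulting positive test to vaccination. Whether this happened, and how often, cannot be settled from the documents.

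The conclusion rests on two assumptions: that some products contain enough anti-spike IgG to turn the test positive, and that some non-responders receive them between day 0 and the sample. If either fails, the bias is zero. If both hold, patient proportions rise and the difference from controls shrinks, with limited scope at 2 weeks and more at 3 to 36 months. The 61% to 47% range for CLL illustrates the mechanism and is not an estimate.

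That controls are unaffected is a reasonable inference from inclusion criterion 2b, which requires no immunosuppressive disease or treatment and no significant co-morbidity; the protocol does not state it. This is an inexpensive safeguard for interpretation and does not invalidate the primary comparison.

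**What to change.** - **6.3.2:** keep the primary analysis. Add a sensitivity analysis excluding participants with ongoing immunoglobulin at baseline or any immunoglobulin between day 0 and the 2-week sample.
- **6.3.3 and 6.3.4:** report the 3 to 36 month proportions separately by immunoglobulin use. Label positives in users as IgG positive, not as seroconverted.
- **Data:** identify users from the existing medication entries, supplemented by medical records for past visits. At remaining visits, note ongoing as well as newly initiated courses, with the date of the last dose.
- **3.2 and 5.5.9:** add infused antibody as a possible source of a positive test.

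The cost is some record review, since 2.1 shows that the 2-week results are reported and that data to 12 months have been collected, plus one additional row or split per table. The sensitivity analysis will have fewer evaluable participants, mainly in primary immunodeficiency and possibly in CLL. No treatment rule changes.

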5.1.4. Exclusion criteria

1. Previous or ongoing COVID-19.
2. Has coagulation disorders, other conditions associated with prolonged bleeding time, or anticoagulant treatments, which, according to the investigator, contraindicate intramuscular injection. Conditions that can be corrected with measures such as treatment with platelet concentrates, coagulation factors, or other measures for people on anticoagulants are not exclusion criteria.
3. Planned to receive another vaccine within 14 days prior to the first dose of the study vaccine, or during the period from the first dose of the study vaccine until 14 days after the second dose of the study vaccine, and vaccination with another vaccine that, in the investigator's opinion, cannot be planned outside these time periods.
4. Pregnancy or breastfeeding.
5. Hypersensitivity to the active substance or to any of the excipients contained in the vaccine.
6. Individuals who are unable to understand the research subject information. Individuals who, for other reasons, are deemed by the investigator to be unsuitable for inclusion.

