- Sampling for SARS-CoV-2 serology and more detailed analyses of humoral immunity (blood).
- Sampling for humoral immunity (saliva).
- Sampling for SARS-CoV-2 PCR test (nasopharynx, NPH).
- Fecal sampling for HIV-infected individuals and controls, for those who have agreed to this part and the sample has not been submitted after the screening visit.
- Sampling for HIV-RNA and HIV-DNA, only for HIV-infected individuals, if this has not been taken during the screening visit.

- Vaccine dose 1 is administered (unless contraindications have been identified following health declaration questions).
- Study participants remain at the healthcare facility for at least 15 minutes (30 minutes for those with bleeding disorders) after vaccination.
- A diary is given to the study participant/information about the eDiary.

Sampling group B:

- Review of health declaration questions in Vaccinate, according to care routine.
- Vital parameters: Blood pressure, pulse, temperature, and respiratory rate are measured. If the temperature is \geq 38 degrees, the study participant is rescheduled for the vaccine dose on another day, when the person has been fever-free for at least 48 hours.
- Review of new medications since the screening visit (unless the screening visit is on the same day as day 1).
- For women of childbearing age, a pregnancy test is performed using a urine sample if this has not been done during the screening visit.
- Clinical laboratory tests including blood count (hemoglobin, white blood cells, and platelets) and differential count (neutrophils, lymphocytes, monocytes, basophils, and eosinophils), liver function (ALT, AST, bilirubin, ALP), creatinine, and IgG analysis, if not taken at the screening visit.
- Testing for SARS-CoV-2 serology and more detailed analyses of humoral immunity (blood).
- Sampling for humoral immunity (saliva).
- Sampling for analysis of cellular immunity (blood).
- Sampling for SARS-CoV-2 PCR test (nasopharynx, NPH).
- Sampling of faeces for HIV patients and controls, for those who have agreed to this part and samples have not been submitted after the screening visit.
- Sampling for HIV-RNA and HIV-DNA, only for HIV patients if this has not been done during the screening visit.
- Vaccine dose 1 is given (unless contraindications have emerged after health declaration questions).
- Study participants remain at the healthcare facility for at least 15 minutes (30 minutes for haemophiliacs) after vaccination.

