¹ Includes blood count (hemoglobin, white blood cells, and platelets) and differential count (neutrophils, lymphocytes, monocytes, basophils, and eosinophils), liver function (ALT, AST, bilirubin, ALP), and creatinine.

IgG analysis in blood only at screening. If the screening visit is conducted via video contact, these samples will be taken on day 0, before the injection of the first vaccine dose.

² Samples will be taken before vaccination.

³ Blood samples can be submitted at Karolinska University Laboratory's sampling units in Stockholm, and study participants do not need to be at the study unit. Saliva samples can be sent by mail.

⁴ During screening visits, previous medications/treatments are noted in accordance with 5.5.2. All medications are noted during screening visits. During the period from the day of the vaccine dose until 14 days after, all medications are recorded after each vaccine dose. During other periods during the study, only new immunosuppressive/immunoglobulin treatments are noted, in accordance with 5.5.2.

⁵ Targeted examinations for symptoms during the study period, if necessary.

⁶ Blood pressure, pulse, temperature, and respiratory rate are measured.

⁷ Diary is issued on day 0/study participants receive an e-diary.

⁸ AE is monitored from the first and second vaccine doses until 14 days after each vaccine dose.

⁹ SAE/SUSAR is monitored within the period from the first vaccination day to 6 weeks after the second vaccine dose.

¹⁰ Nasopharynx sample on day 0 and, if necessary, in case of COVID-19 symptoms. COVID-19 symptoms are: cough, fever \geq 38 degrees, breathing difficulties, runny nose, nasal congestion, sore throat, headache, nausea, muscle and joint pain, impaired sense of smell and taste, or diarrhea.

¹¹ If the screening visit takes place via video contact, a pregnancy test will be performed on day 0, before the first vaccine dose is administered.

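### The primary seroconversion analysis screens out prior infection by baseline serology alone and does not use the day-0 PCR on which the protocol's attribution to the vaccine relies

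*Combined protocol and SAP*

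**What the plan says.** Section 6.2 defines the two-dose population by receipt of both doses and a test result 2 weeks after the second. Section 6.3.2 adds one condition: "having a negative SARS-CoV-2 serology test result at baseline, i.e., seroconverting". (Section 6.3.2 puts the sample at three weeks, where sections 4.2 and 6.2 say two. That is a separate matter, and I use 2 weeks here.) No analysis set carries a PCR condition.

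On eligibility, section 5.1.4 excludes "Previous or ongoing COVID-19" and attaches no test to it. Section 5.2.2 states: "If study participants meet all inclusion criteria and no exclusion criteria, they can proceed to day 0", and it allows screening and day 0 on the same date. Table 2 marks the eligibility check at both screening and visit 1.

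The PCR schedule is in the footnotes to Table 2: "Nasopharynx sample on day 0 and, if necessary, in case of COVID-19 symptoms", and "Samples will be taken before vaccination". None is scheduled at screening. In section 5.2.2 the condition on the first dose refers to the health questions: "Vaccine dose 1 is administered (unless contraindications have been identified following health declaration questions". The day-0 procedures do not say that the PCR result is known by then.

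Section 3.2 says that the IgG test cannot tell infection from vaccination. It answers this by citing baseline serology, baseline PCR and symptom-driven PCR, and concludes that "it is highly likely that those who seroconvert without a diagnosis of COVID-19 do so because of vaccination". Section 5.5.9 repeats the limitation of the test.

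**The concern.** Section 3.2 gives the argument for reading IgG positivity as a vaccine effect, and it has two parts: no antibodies at the start, and no COVID-19 diagnosis. Section 6 carries over the first part and drops the second. The day-0 PCR is collected but has no role in the analysis that it was meant to protect.

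Someone sampled early in an infection can be PCR-positive and still seronegative. Under sections 6.2 and 6.3.2 that person stays in the primary set after both doses and counts as a seroconverter if IgG-positive at 2 weeks. The primary objective in section 4.1 is the immunological effect of Comirnaty, so this is a misattribution.

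It runs in one direction. Infection can change the outcome only in a person who would not have responded to the vaccine. Such people are common in some patient groups and rare among controls, so the patient rate rises and the patient-control difference narrows.

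**Working it through.** **The plan's own figure.** Section 6.1 claims power above 80% at N = 540, α = 0.05 and effect size 0.15. The effect-size metric is not defined. Read as Cohen's w with 1 degree of freedom, the noncentrality is 540 × 0.15² = 12.15 and the power is 93.6%, so the claim is reproduced under that reading. The point below does not depend on it; I use it only to price the fix.

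**Who is affected.** All four conditions must hold: PCR-positive on day 0, seronegative on day 0, both doses received, and IgG-positive at 2 weeks. Bias arises only from those who would otherwise have been IgG-negative.

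**Inputs.**
- True vaccine response p. Illustrative values come from the version 5.0 addition in section 2.1: 43% in organ transplant recipients, 63% in CLL, 72% in all patients.
- Share f that is PCR-positive and seronegative on day 0. The documents do not give it. Assumption: 0.5% to 5%, which is 90 × 0.005 = 0.45 to 90 × 0.05 = 4.5 people per group of 90.
- All infected non-responders become IgG-positive. This assumption makes the result an upper limit for each f.
- Infection on day 0 is unrelated to vaccine response.

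**Formula.** Observed rate = p + f(1 − p), so inflation = f(1 − p).

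| Group | 1 − p | f = 0.5% | f = 5% |
|---|---|---|---|
| Organ transplant | 0.57 | 0.29 points | 2.85 points |
| CLL | 0.37 | 0.18 points | 1.85 points |
| All patients | 0.28 | 0.14 points | 1.40 points |

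**Controls.** Section 2.1 reports a 60-fold lower chance of seroconversion in patients. If that is read as an odds ratio (an assumption), the control odds are (0.72/0.28) × 60 ≈ 154, a rate of about 99%. With 1 − p then about 0.006, inflation at f = 5% is 0.05 × 0.006 = 0.0003, or 0.03 points.

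**If the reported rates already contain such infections.** The true rate would then be (observed − f)/(1 − f). At 43% and f = 5% this is 0.38/0.95 = 40.0%, an inflation of 3.0 points, so the answer barely moves.

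**Scale.** The 95% CI half-width for 43% at n = 90 is 1.96 × √(0.43 × 0.57/90) = 10.2 points.

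**Cost in power.** Removing 0.5% to 5% of 540 takes out 3 to 27 people. The noncentrality becomes 537 × 0.0225 = 12.08 down to 513 × 0.0225 = 11.54, and power 93.5% down to 92.5%, against 93.6%.

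**Infections after day 0.** Suppose that 5% of non-responders, and no responders, have a PCR-confirmed infection before the 2-week sample, with a true rate of 43%. The affected share is 0.05 × 0.57 = 0.0285. Removing them gives 0.43/(1 − 0.0285) = 44.3%, which is 1.3 points too high. Keeping them gives between 43.0% (none has turned IgG-positive by then) and 45.9% (all have). Neither choice is free of bias.

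**The case against.** The strongest case on the other side is that the effect is small and that exclusion 1 already expresses the intent.

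- **Size.** This stands. Even the extreme of the assumed range is well inside the 10-point half-width. The assumed f may also be generous: section 3.2 has people with COVID-19 symptoms told not to come to the hospital, and section 5.2.2 reschedules anyone with a temperature of 38 degrees or more. A reader might infer that the patient-control comparison is in doubt. The figures do not support that, because 2.9 points is little beside a gap of more than 50 points between 43% and a control rate near 99%.
- **Exclusion 1.** This stands in part. A reader might infer that the protocol makes the day-0 PCR the test for ongoing COVID-19 and then doses people before that test can work. The documents do not say so. Section 5.1.4 names no test, same-day screening is allowed, and eligibility is checked again at visit 1. A positive day-0 result would look like an eligibility deviation. What is missing is any rule for such a person in the analysis sets.
- **Breadth.** A reader might infer that every PCR-positive participant counts as a vaccine seroconverter. Only those who meet all four conditions do, and those who would have responded anyway add no bias.
- **Later infections.** It is tempting to drop everyone with a positive PCR before the 2-week sample from the primary set. That conditions on an event after baseline, found by symptom-driven testing. Fever, headache, and muscle and joint pain both trigger a PCR (section 5.3.5) and are solicited vaccine reactions (section 5.8.3), so testing may differ between groups, and asymptomatic infection is missed. The working shows that removal can itself raise the patient rate.

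**Conclusion.** The gap is real and the likely effect is small. Sections 6.2 and 6.3.2 omit a condition on which section 3.2 relies, so a participant who is PCR-positive and seronegative on day 0 can be counted as a vaccine seroconverter. At a 43% response rate the inflation is at most about 0.3 to 2.9 points, at 63% about 0.2 to 1.9, and near zero in controls. This rests on an assumed 0.5% to 5% being PCR-positive and seronegative on day 0, on all of them becoming IgG-positive, and on infection being unrelated to vaccine response. The direction follows from the definition of the endpoint; the size cannot be settled from the documents. The point warrants correction because a baseline filter on data already collected removes the problem at almost no cost, not because the main conclusion is at risk.

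**What to change.** 1. In sections 6.2 and 6.3.2, define the primary set as two-dose participants with a 2-week result, negative baseline serology and a negative day-0 PCR. State how a missing PCR result is handled, and report the number removed per group.
2. Keep participants with PCR-confirmed infection between day 0 and the 2-week sample in the primary set, and add a sensitivity analysis that removes them.
3. In section 6.3.3, state that a positive day-0 PCR is not a new diagnosis of infection.
4. Reconcile sections 5.1.4 and 5.2.2 and Table 2 on how exclusion 1 is ascertained and how the day-0 PCR relates to the eligibility check.

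The cost is a few lines of text and one filter on existing data. A few participants leave the primary set, with power falling by about one point at most on the reading above. Because section 2.1 already reports 2-week results, a re-analysis of them with this filter should be labelled post hoc.
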